3 SCHEDULE OF ASSESSMENTS

Table 3-1 and **Table 3-2** provide the schedules of assessments. All visits are to be scheduled relative to the Day 1 Visit in each Part.

The Cystic Fibrosis Questionnaire-Revised (CFQ-R) must be completed before any other assessment (except informed consent form [ICF] signing) at relevant clinic visits. Multiple breath washout (MBW) assessments should be performed before spirometry, and ECG should be performed before any assessments that may affect heart rate (such as blood draws). Remaining assessments may be performed in any order when more than 1 assessment is required at a particular time point. All assessments will be performed before study drug dosing (Section [9.6.1](#)), unless noted otherwise.

Table 3-1 Study VX19-445-107: Part A Treatment Period and Safety Follow-up Visit

Event/Assessment ^a	Part A Treatment Period (96 weeks)						Part A ETT Visit ^b	Part A Safety Follow-up Visit ^c (28 ± 7 Days After Last Dose of Study Drug)	Comments
	Day 1 ^d	Weeks 8, 16, 24, 36 (± 5 Days)	Weeks 4, 12, 20, 28, 32, 40, 44, 52, 56, 64, 68, 76, 80, 88, 92 (± 5 Days)	Week 48 (± 5 Days)	Weeks 60, 72, 84 (± 5 Days)	Week 96 ^e (± 5 Days)			
Clinic visit	X	X		X	X	X	X	X	
Telephone contact			X						When telephone contact takes the place of a clinic visit, a urine pregnancy test will be performed with a home kit provided by the study site (Section 11.5.2).
Informed consent and assent	X								
Inclusion and exclusion criteria confirmation	X								See Section 8 for details.
CFQ-R	X	Weeks 8, 24		X	Week 72	X	X	X	To be completed before any other assessments scheduled at relevant visits (Section 11.3.5).
Ophthalmologic examination				X		X	X		Subjects will have an ophthalmologic examination at Week 48 and at Week 96 (Section 11.5.5). In addition, an ophthalmologic examination will be performed at the ETT Visit for subjects who discontinue study drug if the subject has received at least 12 weeks of study drug since their last study ophthalmologic examination.
Full physical examination	X					X	X		Symptom-directed physical examinations will be performed at any time if deemed necessary by the investigator or healthcare provider (Section 11.5.3).
Weight, height, and BMI	X	X		X	X	X	X	X	Weight and height measured with shoes off (Section 11.3.4).

^a All assessments will be performed before study drug dosing unless noted otherwise.

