Blood biomarker sample	X			X		X	X		Section 11.4.2

^e Subjects whose Part B Day 1 Visit is on the same day or within 1 calendar day as the Part A Week 96 Visit do NOT have to repeat any Part B Day 1 assessments that were specified to be performed at the Part A Week 96 Visit. Subjects whose Part B Day 1 Visit is more than 1 calendar day after the Part A Week 96 Visit must complete all assessments specified for the Part A Week 96 AND Part B Day 1 Visits.

Table 3-1 Study VX19-445-107: Part A Treatment Period and Safety Follow-up Visit

Event/Assessment ^a	Part A Treatment Period (96 weeks)						Part A ETT Visit ^b	Part A Safety Follow-up Visit ^c (28 ± 7 Days After Last Dose of Study Drug)	Comments
	Day 1 ^d	Weeks 8, 16, 24, 36 (± 5 Days)	Weeks 4, 12, 20, 28, 32, 40, 44, 52, 56, 64, 68, 76, 80, 88, 92 (± 5 Days)	Week 48 (± 5 Days)	Weeks 60, 72, 84 (± 5 Days)	Week 96 ^e (± 5 Days)			
FE-1	X	Week 24		X		X	X		Samples may be collected by the subject's caregiver up to 24 hours before the study visit (e.g., at home). The sample may be collected pre- or postdose (Section 11.4.1).
IRT	X	Week 24		X	Week 72	X	X		Section 11.4.1
Study drug dosing	Day 1 through evening before Week 96 Visit								Subjects on study drug interruption at the end of the parent study may not begin dosing until they meet the criteria in Section 9.8. Refer to Section 9.6.1 for study drug administration details.
Study drug count		X		X	X	X	X		
Other events related to outcome	Continuous from signing of ICF through completion of study participation								Includes PEx, administration of antibiotic therapy for sinopulmonary signs/symptoms, and hospitalizations for CF (Section 11.3.6). Completion of study participation is defined in Section 9.1.5.
Medications review	Continuous from signing of ICF through completion of study participation								Completion of study participation is defined in Section 9.1.5.
Treatment and procedures review	Continuous from signing of ICF through completion of study participation								Completion of study participation is defined in Section 9.1.5.
AEs and SAEs	Continuous from signing of ICF through completion of study participation								Completion of study participation is defined in Section 9.1.5.

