9.2 Analysis Period for Part A Analysis

OLE Efficacy Period for Part A: Time from the first dose of study drug in the corresponding Part until the last efficacy assessment, which may be collected up to the corresponding Week 96 Visit or the earlier of Day 673 and the end of study participation if subject does not have the corresponding Week 96 Visit in the same Part. This analysis period will be used with the OLE-FAS for the corresponding Part to analyze efficacy data during the corresponding Part.

OLE Safety Period for Part A: Time from the first dose of study drug in the corresponding Part to 28 days after the last dose of the study drug in the corresponding Part or to the completion date of study participation (as defined in Section 9.1.5 of the CSP), whichever occurs first.

The completion date of study participation will be obtained from the end of study page of the eCRF.

The **Treatment-emergent (TE) Period for Part A** is same as the OLE Safety Period for the corresponding Part.

Cumulative TC Efficacy Period for Part A: For subjects who enrolled in Part A, the time from the first dose of study drug in the parent study (445-106 Part B) until the last efficacy assessment in Part A, which may be collected up to the Part A Week 96 Visit or the earlier of Day 673 in Part A and the end of study participation if subject does not have the Part A Week 96 Visit. For subjects who did not enroll in the OLE study and were enrolled and received study drug in the parent study, definition of this analysis period is the same as the parent study efficacy period.

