9.3 Analysis Period for Final Analysis

OLE Efficacy Period: Time from the first dose of study drug in the OLE study to the last efficacy assessment, which may be collected up to OLE Part B Week 96 Visit or the earlier of Day 1345 and the end of study participation if subject does not have the OLE Part B Week 96. This analysis period will be used with the OLE-FAS to analyze efficacy data in the Week 144 IA and the final analysis.

OLE Safety Period: Time from the first dose of study drug in the OLE study to 28 days after the last dose of the study drug in the OLE study or to the completion date of study participation (as defined in Section 9.1.5 of the CSP), whichever occurs first.

The completion date of study participation will be obtained from the end of study page of the eCRF.

The **OLE Treatment-emergent (TE) Period** is same as the OLE Safety Period.

The OLE Cumulative TC Efficacy Period: For subjects who enrolled in the OLE study, the time from the first dose of study drug in the parent study (445-106 Part B) until the last efficacy assessment in the OLE study, which may be collected up to the Part B Week 96 Visit or the earlier of Day 1345 and the end of study participation if subject does not have the Part B Week 96 Visit. For subjects who did not enroll in the OLE study and were enrolled and received study drug in the parent study, definition of this analysis period is the same as the parent study efficacy period.

The Cumulative TC Efficacy periods will be used with the Cumulative TC sets for analysis of PEx data.

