For all continuous endpoints, to better assess the longitudinal profile of the efficacy and pharmacodynamics assessments with repeated measures up to OLE Part B Week 96, the LS means (\pm SE) for absolute change from baseline at each visit will also be plotted. In addition, the post-baseline raw values and the absolute change from baseline at each post-baseline visit will be summarized descriptively (n, mean, SD, median, minimum, and maximum).

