a. If no numerical measurement is available within a visit window, the measurement will be considered missing for the visit.			
b. If there is more than 1 numerical measurement available within a visit window, use the following rules:			
i. The measurement closest to the target day will be used; or			
ii. If there are multiple measurements with the same distance from the target day, the latest measurement will be used. If the latest measurement cannot be determined, then unscheduled visit will be selected.			
³ For measurement collected on the date of first dose of study drug in Treatment Period, if it cannot be determined whether the measurement is before or after the first dose:			
1. Scheduled measurement will be treated as pre-dose observation.			
2. Unscheduled measurement will be treated as post-dose observation.			
⁴ For safety Assessment, Safety Follow-up analysis visit will be based on nominal Safety Follow-up visit. If a subject doesn't have a nominal Safety Follow-up visit but has an ETT visit with study day >687, then the ETT visit will be mapped into Safety Follow-up analysis visit.			
⁵ For efficacy assessment, if a subject has nominal safety follow up visit with study day >687, then nominal Safety Follow-up visit will be mapped to Safety Follow-up visit; else if subject doesn't have a nominal safety follow-up visit with study day > 687 but has an ETT visit with study day >687, then the ETT visit will be mapped into Safety Follow-up analysis visit; else if there are multiple assessments with >687 then select the earliest record.			
Derived Variables:			

Table 13-1 Analysis Visit Windows for Safety and Efficacy Assessments for Part A			
Assessment	Visit¹	Target Study Day	Analysis Visit Window (in study days)²
1. Age (in years) at first dose date and post-baseline visit (for demographics, listing and the calculation of [percent] predicted spirometry variables):			
Obtain the age at informed consent in “yy, mm” format (e.g., 24 years, 6 months) in parent study from the Vital Signs (VS) page at the Screening Visit in parent study and add 0.5 month to convert to days.			
Obtain the informed consent date in parent study.			
Then age (in years) at first dose or post-baseline visit = [(first dose date or post-baseline visit date – informed consent date in parent study) in days + age at informed consent (in days) in parent study]/365.25.			
2. Age (in months) at first dose date and post-baseline visit (for use in calculation of BMI):			

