Standard 12-lead ECG	Baseline	1	defined in section 8.1
Coagulation	OLE Part A Week 24	169	[1, 253]
	OLE Part A Week 48	337	(253, 421]
	OLE Part A Week 72	505	(421, 589]
	OLE Part A Week 96	673	(589, 757]
	OLE Part B Week 24	841	(757, 925]
	OLE Part B Week 48	1009	(925, 1093]
	OLE Part B Week 72	1177	(1093, 1261]
	OLE Part B Week 96	1345	(1261, 1359]
	Safety Follow-up ⁴	Not applicable	Use nominal visit
Efficacy Assessment⁵			
Part A: same as in Table 13-1			
Part B: see below			

Table 13-2 Analysis Visit Windows for Safety and Efficacy Assessments for the OLE study			
Assessment	Visit¹	Target Study Day	Analysis Visit Window (in study days)²
Spirometry Weight, Height and BMI (and the corresponding z-scores)	Baseline	1	defined in section 8.1
	OLE Part B Week 12	757	(667, 799]
	OLE Part B Week 24	841	(799, 883]
	OLE Part B Week 36	925	(883, 967]
	OLE Part B Week 48	1009	(967, 1051]
	OLE Part B Week 60	1093	(1051, 1135]
	OLE Part B Week 72	1177	(1135, 1219]
	OLE Part B Week 84	1261	(1219, 1303]
	OLE Part B Week 96	1345	(1303, 1401]
	Safety Follow-up ⁶	Not applicable	>1401
CFQ-R	Baseline	1	defined in section 8.1
	OLE Part B Week 24	841	(667, 925]
	OLE Part B Week 48	1009	(925, 1093]
	OLE Part B Week 72	1177	(1093, 1261]
	OLE Part B Week 96	1345	(1261, 1401]
	Safety Follow-up ⁶	Not applicable	>1401
Sweat chloride Lung Clearance Index IRT	Baseline	1	defined in section 8.1
	OLE Part B Week 24	841	(667, 925]
	OLE Part B Week 48	1009	(925, 1093]
	OLE Part B Week 72	1177	(1093, 1261]
	OLE Part B Week 96	1345	(1261, 1401]
FE-1	Baseline	1	defined in section 8.1
	OLE Part B Week 48	1009	(667, 1177]
	OLE Part B Week 96	1345	(1177, 1401]
Notes:			
^{1,2,3} : See Table 13-1 .			
⁴ For safety Assessment, Safety Follow-up analysis visit will be based on nominal Safety Follow-up visit. If a subject doesn't have a nominal Safety Follow-up visit but has a Part A ETT visit with study day >687 or a Part B ETT visit with study day >1359, then the ETT visit will be mapped into Safety Follow-up analysis visit.			
⁵ For efficacy windowing rules, Part A data will only be used to derive Part A analysis visits using the window rules in Table 13-1 . Part B data will only be used to derive Part B analysis visits using the window rules in this table. Note that Safety Follow-up visits from both Parts will be combined for efficacy summary tables.			

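### The final efficacy tables merge Part A and Part B Safety Follow-up values about 1.84 years apart into one row, and the windows that fill that row are faulty in both Parts

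*SAP*

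**What the plan says.** SAP Appendix A, Table 13-2, footnote 5 derives Part A analysis visits from Part A data only and Part B visits from Part B data only, then makes one exception: "Note that Safety Follow-up visits from both Parts will be combined for efficacy summary tables". Safety Follow-up rows exist for spirometry, weight, height, BMI, their z-scores and CFQ-R. There is none for sweat chloride, LCI, IRT or FE-1. SAP 10.3.2.2.2 adds that "the post-baseline raw values and the absolute change from baseline at each post-baseline visit will be summarized descriptively", so the row will carry both raw values and changes.

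The separation by Part is otherwise consistent. Protocol 12.3.3.2 analyses the secondary endpoints by Part, and Protocol 12.3.1 allows events to be combined only for the number of pulmonary exacerbations. SAP 10.3.2 fits separate repeated-measures models to Parts A and B. SAP 3.1, which lists departures from the protocol, declares pooling of safety data only.

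On windows, the Part A efficacy Week 96 window in Table 13-1 (spirometry and growth) is (631, 687], and the Safety Follow-up row is >687. Footnote 5 of that table fills the row first from a nominal follow-up visit after Day 687, then from an early-termination (ETT) visit after Day 687; "else if there are multiple assessments with >687 then select the earliest record". For Part B, the table gives Week 96 as (1303, 1401] and Safety Follow-up as >1401. Footnote 6 instead maps nominal follow-up and ETT visits after Day 1359 to Safety Follow-up.

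**The concern.** A summary row is readable when its values share a time origin or a time point. Here the values share the time since stopping drug, but the change is counted from the parent-study baseline, in children who entered that study at 6 through 11 years of age. For measures that rise with growth, the row's mean and SD partly reflect how many values came from each Part. A reader cannot separate that from what happens after stopping treatment.

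The windows raise a second problem. If a late Part A Week 96 value is filed under Safety Follow-up, an on-drug measurement is reported as off-drug and is also missing from the Part A Week 96 estimate. If the Part B cut-off is ambiguous, two programmers working from the same SAP would fill the row differently.

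**Working it through.** **Inputs.** Week 96 targets are Day 673 (Part A) and Day 1345 (OLE), from SAP 9.2 ("or the earlier of Day 673 and the end of study participation"), SAP 9.3 ("or the earlier of Day 1345 and the end of study participation") and Tables 13-1 and 13-2. Follow-up is "28 ± 7 Days After Last Dose of Study Drug" (Protocol Tables 3-1 and 3-2). Dosing runs "Day 1 through evening before Week 96 Visit". The Week 96 visit window is ±5 days.

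**Target days reproduced.** 96 × 7 + 1 = 673 and 192 × 7 + 1 = 1345, as stated.

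**Follow-up days.** Last dose is the day before Week 96, so follow-up = Week 96 day − 1 + 28.
- Part A: 673 − 1 + 28 = Day 700. Range 668 − 1 + 21 = 688 to 678 − 1 + 35 = 712.
- Part B: 1345 − 1 + 28 = Day 1372. Range 1340 − 1 + 21 = 1360 to 1350 − 1 + 35 = 1384, or 1355 to 1389 if the ±5-day windows of both Parts accumulate.

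**Gap.** 1372 − 700 = 672 days; 672 / 365.25 = 1.84 years. Using the footnote 6 cut and the visit windows, the gap runs from (1360 − 712) / 365.25 = 1.77 to (1389 − 688) / 365.25 = 1.92 years.

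**Effect on growth measures.** The documents give no growth rates and no Part A share. The assumptions are 4 to 7 cm and 2 to 5 kg a year, equal growth in both sources, and a Part A share p of 20%, 50% or 80%. The difference between sources is d = rate × 1.84: 7.4 to 12.9 cm and 3.7 to 9.2 kg. Relative to an all-Part-B row the mean falls by p × d. The between-source component of the SD is √(p(1 − p)) × d.

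| Part A share | Mean height change lower by | Mean weight change lower by | Between-source SD, height |
|---|---|---|---|
| 20% | 1.5 to 2.6 cm | 0.7 to 1.8 kg | 2.9 to 5.2 cm |
| 50% | 3.7 to 6.4 cm | 1.8 to 4.6 kg | 3.7 to 6.4 cm |
| 80% | 5.9 to 10.3 cm | 2.9 to 7.4 kg | 2.9 to 5.2 cm |

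The same direction applies to raw BMI and litre-based spirometry, but no size is computed for them.

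**Late Part A Week 96 visits.** Day 688 is 688 − 673 = 15 days after target and 688 − 678 = 10 days outside the protocol window. Windows are applied by study day to scheduled and unscheduled visits alike, so such a visit leaves Week 96. It enters the follow-up row if the child has no nominal follow-up or ETT visit after Day 687. A child who moves to Part B within 28 days is typically in that position, because Protocol 9.1.2 then waives the Part A follow-up visit. That child can later supply a Part B follow-up value as well, and no rule chooses between the two. SAP 9.2 extends the Part A efficacy period up to the Week 96 visit, so it counts this same value as within the period. Other windows are wider: Part B efficacy Week 96 runs 1401 − 1345 = 56 days past target, and the OLE safety windows for Part A Week 96 run to Day 715 or Day 757.

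**Part B cut-off.** Under footnote 6, Day 1372 is follow-up. Under the table row it lies in Week 96, and since 1389 < 1401 no on-schedule Part B follow-up visit reaches the row. The closest-to-target rule would normally still choose the true Week 96 visit. An off-drug value would stand in for Week 96 only when nothing closer to Day 1345 exists.

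**The case against.** A reader might infer that the merged row has no meaning at all. The documents do not support that. Each subject's change from baseline stays defined. ppFEV₁ is computed from age and height (SAP Appendix C), and the z-scores are adjusted for age and sex (SAP 10.3.1.2.1), so the growth argument largely does not reach them. Nominal follow-up visits in both Parts are timed the same way relative to the last dose, so aligning on time since stopping is a defensible descriptive idea.

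A reader might also infer that this is the only off-drug summary. It is not: the separate Part A analysis under Table 13-1 has its own unmerged follow-up row, and SAP 10.3.2 keeps measurements after discontinuation in the other visit windows.

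Nor do the documents show that late on-drug visits are common. They need a visit on Day 688 or later, and the number is not given. The earliest-record clause reads as a tie-break; what admits a single late record is the >687 row. Contributors from Part A may be few, because moving within 28 days to Part B, to a commercial regimen or to managed access waives the visit.

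Finally, the stakes are limited. This is one descriptive row for secondary endpoints, no objective concerns the effect of stopping, and no model text includes Safety Follow-up.

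All of this stands and narrows the point. It does not remove the undeclared departure from analysis by Part, the dependence of the raw growth rows on the mix, or the two window faults.

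**Conclusion.** The point holds for raw height, weight, BMI and litre-based spirometry in the final OLE descriptive tables. One row would combine values 1.84 years apart, contrary to the protocol's analysis by Part and without being listed as a modification. On the assumed growth rates the two sources differ by about 7 to 13 cm and 4 to 9 kg. How far the row's mean moves depends on a Part A share that the documents do not give.

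These sizes rest on footnote 6 governing Part B. If the >1401 row governs instead, on-schedule Part B visits never enter and the supposedly combined row is almost entirely Part A. Either way the SAP does not settle what the row contains.

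The late-visit fault is conditional but real. A Part A Week 96 value on Day 688 or later is lost from Week 96, and it is labelled follow-up when no nominal follow-up or ETT visit after Day 687 exists. ppFEV₁ and the z-scores are much less affected by the merge. The unmerged Part A table and the primary safety endpoint are not affected by it.

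**What to change.** Four changes to SAP Appendix A:

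1. In Table 13-2, replace the combined row with separate Part A and Part B Safety Follow-up rows and delete the combining sentence in footnote 5.
2. Fill each row only from the nominal Safety Follow-up visit, or from an ETT visit that replaces it under Protocol 9.1.2 and 9.1.3 (3 weeks or later after the last dose).
3. Change the >687 window itself, not only the tie-break clause, so that a nominal Part A Week 96 visit done on drug maps to Part A Week 96.
4. Reconcile >1359 with >1401 so that the table and footnote 6 agree and off-drug Part B follow-up visits do not enter Week 96.

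The rule in SAP 10.3.2 that keeps post-discontinuation measurements in earlier visit windows can stay. If the sponsor prefers to keep a combined row, it should be declared in SAP 3.1 and limited to the age-adjusted measures.

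The cost is SAP wording and one extra descriptive row, with no new data. The Part A row will probably have a small n, which is itself useful to show.

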	Day 1 ^d	Weeks 4, 8, 16, 20, 28, 32, 40, 44, 52, 56, 64, 68, 76, 80, 88, 92 (± 5 Days)	Weeks 12, 36, 60, 84 (± 5 Days)	Weeks 24, 48, 72 (± 5 Days)	Week 96 (± 5 Days)			
Study drug dosing	Day 1 through evening before Week 96 Visit							Subjects on study drug interruption at the end of the parent study may not begin dosing until they meet the criteria in Section 9.8. Refer to Section 9.6.1 for study drug administration details.
Study drug count			X	X	X	X		
Other events related to outcome	Continuous from signing of ICF through completion of study participation							Includes PEx, administration of antibiotic therapy for sinopulmonary signs/symptoms, and hospitalizations for CF (Section 11.3.6). Completion of study participation is defined in Section 9.1.5.
Medications review	Continuous from signing of ICF through completion of study participation							Completion of study participation is defined in Section 9.1.5.
Treatment and procedures review	Continuous from signing of ICF through completion of study participation							Completion of study participation is defined in Section 9.1.5.
AEs and SAEs	Continuous from signing of ICF through completion of study participation							Completion of study participation is defined in Section 9.1.5.

AE: adverse event; BMI: body mass index; CF: cystic fibrosis; CFQ-R: Cystic Fibrosis Questionnaire-Revised; ETT: Early Termination of Treatment; FE-1: fecal elastase-1; ICF: informed consent form; IRT: immunoreactive trypsinogen; PEx: pulmonary exacerbation; SAE: serious adverse event

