10.3.2 Efficacy Analysis for the OLE study

All efficacy analyses described in this section will be based on the OLE-FAS, unless otherwise specified. The analysis will include all available measurements through the last scheduled visit in the OLE study, including measurements after treatment discontinuation.

Continuous endpoints during the parent study will be analyzed using the same mixed-effects model for repeated measures (MMRM) approach as described in the SAP for the parent study. The resulting estimates will be identical to what is available in the final CSR of the parent study. Similarly, continuous endpoints during the OLE efficacy period will also be analyzed using separate MMRM models for Parts A and B, so that Part A data will be analyzed consistently as what was done in the Part A analysis and the resulting estimates will be identical to the Part A analysis results. The results obtained from the parent study and the OLE efficacy period will be displayed one followed by the other.

There is no multiplicity adjustment.

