⁶ For efficacy assessment in Part B, if a subject has nominal Part B safety follow up visit with study day >1359, then nominal Safety Follow-up visit will be mapped to Safety Follow-up visit; else if subject doesn't have a nominal safety follow-up visit with study day >1359 but has an ETT visit with study day >1359, then the ETT visit will be mapped into Safety Follow-up analysis visit; else if there are multiple assessments with >1401 then select the earliest record.			
Derived Variables: See Table 13-1 .			

Table 13-3 Efficacy Analysis Visit Windows for Week 144 Interim Analysis if Extended OLE Part B Week 48 is used.			
Assessment	Visit	Target Study Day	Analysis Visit Window (in study days)
Efficacy Assessment			
Part A: same as in Table 13-1			
Part B: see below			
Spirometry Weight, Height and BMI (and the corresponding z-scores)	Baseline OLE Part B Week 12 OLE Part B Week 24 OLE Part B Week 36 Extended OLE Part B Week 48	1 757 841 925 1009	defined in section 8.1 (667, 799] (799, 883] (883, 967] >967
CFQ-R	Baseline OLE Part B Week 24 Extended OLE Part B Week 48	1 841 1009	defined in section 8.1 (667, 925] >925
Sweat chloride Lung Clearance Index	Baseline OLE Part B Week 24 Extended OLE Part B Week 48	1 841 1009	defined in section 8.1 (667, 925] >925
Notes: The above analysis windows will be used only when mitigation plans regarding the impact of COVID-19 pandemic will be implemented. See Section 11.1.2 for details.			
See Table 13-1 table notes for detailed.			

▪ Appendix B: Imputation Rules for Missing Prior/Concomitant Medication Dates

Imputation rules for missing or partial medication start/stop dates are defined below:

1. Missing or partial medication start date:
 - a. If only DAY is missing, use the first day of the month.
 - b. If DAY and Month are both missing, use the first day of the year.
 - c. If DAY, Month and Year are all missing, use a date before the first dose date (in practical, use Jan. 01, 2000 to impute).
2. Missing or partial medication stop date:
 - a. If only DAY is missing, use the last day of the month.
 - b. If DAY and Month are both missing, use the last day of the year.
 - c. If DAY, Month and year are all missing, assign ‘continuing’ status to stop date (in practical, use Dec. 31, 2050 to impute).

In summary, the prior, concomitant, or post categorization of a medication is described below.

Table 13-4 Prior, Concomitant, and Post Categorization of a Medication

Medication Start Date	Medication Stop Date		

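### SAP Table 13-2 gives conflicting Week 96 and Safety Follow-up cut-offs for Part B efficacy with no stated precedence; separately, its Part B windows appear to make no allowance for a gap between Parts

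*SAP*

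**What the plan says.** **Part B efficacy windows (SAP Appendix A, Table 13-2).** The Week 96 target is Day 1345. The Week 96 window is (1303, 1401] for spirometry and weight/height/BMI, and (1261, 1401] for CFQ-R. Safety Follow-up is >1401 in both groups.

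**Footnote 6, attached to those Safety Follow-up rows.** Its first branch applies "if a subject has nominal Part B safety follow up visit with study day >1359" and sends that visit to Safety Follow-up. The second does the same for an early-termination (ETT) visit, and the third changes the bound: "with study day >1359, then the ETT visit will be mapped into Safety Follow-up analysis visit; else if there are multiple assessments with >1401".

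**Part A comparator (Table 13-1).** The rows end Week 96 at Day 687, and footnote 5 uses 687 in every branch, ending "else if there are multiple assessments with >687 then select the earliest record".

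**Other rules on the same records.**
- Section 9.3 closes the OLE Efficacy Period with the final scheduled Part B efficacy visit; where that visit is missing, its fallback reads: "or the earlier of Day 1345 and the end of study participation if subject does not have the OLE Part B Week 96".
- Section 10.3.2: "The analysis will include all available measurements through the last scheduled visit in the OLE study, including measurements after treatment discontinuation".
- Table 13-2, footnote 5: "Note that Safety Follow-up visits from both Parts will be combined for efficacy summary tables".

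**Day count.** The SAP does not say in words where Part B study day starts. Section 9.3 applies Day 1345 to a period that begins at the first OLE dose. Section 9.2, in the cumulative period, writes "the earlier of Day 673 in Part A and the end of study participation". Protocol Section 3 schedules visits from Day 1 of each Part. Protocol Section 9.1.1 makes the Part A Week 96 Visit the default Part B Day 1, but provides for a later Part B Day 1 with no stated maximum.

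**Part B Week 96 safety windows.** These are (1303, 1359] for chemistry, hematology and vital signs, and (1261, 1359] for ECG and coagulation.

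**The concern.** A follow-up or ETT record on Days 1360-1401 has two destinations: Week 96 by the row and Safety Follow-up by the footnote. The windows cover scheduled and unscheduled visits alike, and nothing removes a nominal follow-up record from the Week 96 window. Two programmers could therefore place the same spirometry, growth or CFQ-R value differently. Where the Week 96 value is missing, a value taken about 3 to 5 weeks after the last dose could stand in for it.

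The second issue has a different cause. If Part B days continue the Part A count, any delay between Parts shifts every Part B visit later against fixed windows. The final safety window is the tightest, at 14 days past target, so it fails first. By-visit laboratory, vital-sign and ECG summaries support the primary (safety) endpoint.

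**Working it through.** **Inputs.** Part A and Part B Week 96 Visits are each ±5 days (Protocol Tables 3-1 and 3-2). Dosing in each Part runs "Day 1 through evening before Week 96 Visit", so the last dose is the day before. Safety Follow-up is 28 ± 7 days after the last dose (Protocol 9.1.2). Let a and b be the two Week 96 deviations (-5 to +5), c the follow-up deviation (-7 to +7), and g the days from the Part A Week 96 Visit to Part B Day 1.

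**1. The plan's own targets.** Day = 7 × (96 + Part B week) + 1. Week 96 gives 7 × 192 + 1 = 1345, and Part A Week 96 gives 7 × 96 + 1 = 673. All Part B targets (757 to 1345) reproduce, and they assume that Part B Day 1 falls on Day 673.

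**2. Part A cut-off.** 687 = 673 + 14. On-schedule Part A follow-up runs from 668 - 1 + 21 = 688 to 678 - 1 + 35 = 712, so it is always above 687. Part A rows and footnote agree and work.

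**3. Part B cut-offs.** 1359 = 1345 + 14 follows the Part A pattern. 1401 = 1345 + 56 does not.

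**4. On-schedule Part B follow-up with no gap (g = 0).** Week 96 = 1345 + a + b. Follow-up = 1345 + a + b - 1 + 28 + c = 1372 + a + b + c, which runs from 1355 to 1389. There are 11 × 11 × 15 = 1815 combinations:

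| Follow-up day | Combinations | Row | Footnote 6 |
|---|---|---|---|
| 1355-1359 | 35 | Week 96 | not caught |
| 1360-1389 | 1780 | Week 96 | Safety Follow-up |
| above 1401 | 0 | - | - |

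The 35 need a + b + c ≤ -13: for a + b = -10, -9, -8, -7, -6 the counts are 1×5 + 2×4 + 3×3 + 4×2 + 5×1 = 35. These are counts of permitted schedules, not shares of subjects.

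**5. Can follow-up displace an existing on-schedule Week 96 value?** Table 13-1 note 2, carried into Table 13-2, takes the value closest to target and, on a tie, the latest. Follow-up comes 20 to 34 days after Week 96, and Week 96 is at most 10 days from target. Follow-up is never closer. It ties once in 1815: Week 96 on Day 1335, follow-up on Day 1355, each 10 days from 1345.

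**6. Section 9 limits against the rows.** With no Week 96 Visit, the Part B row accepts 1401 - 1345 = 56 days beyond the Section 9.3 limit. Part A shares the mismatch on a smaller scale: 687 - 673 = 14 days beyond Section 9.2.

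**7. Effect of a gap, on a continuous count.** Part B Week 96 = 1345 + a + g + b. It passes 1359 when a + b + g ≥ 15:
- both visits on target: g = 15;
- one visit 5 days late: g = 10;
- both 5 days late: g = 5.

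The safety Follow-up row uses the nominal visit, so such a Week 96 safety value has no window. Efficacy is more tolerant: with visits on target, 12-weekly values move to the next window from g = 43, and Week 96 leaves its row from g = 57.

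**8. Is the count really continuous?** The targets, Section 9.3's Day 1345 and Section 9.2's explicit mention of Part A all point that way. So does the Part B efficacy opening at >667: it admits a Part B Day 1 on Days 668-672, which could not occur on a re-based count. This is inference, not a stated rule.

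**The case against.** **A consistent reading exists.** Footnote 6 can be read as an ordered override: nominal follow-up after 1359, otherwise ETT after 1359, otherwise any other record after 1401. The row would then govern genuine late Week 96 visits. This is plausible, but the SAP does not say it, and it leaves follow-up on Days 1355-1359 in Week 96.

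**Section 9.3 largely closes the harm.** On its face the efficacy period ends at the Week 96 Visit or, failing that, no later than Day 1345. Follow-up would then not reach the Week 96 model whichever row applies. Footnote 5 concerns summary tables and does not say that follow-up enters the model. This stands as a strong limit on consequence. It does not settle the matter: read strictly, Section 9.3 would empty the follow-up row that footnote 5 expects, and Section 10.3.2 takes measurements after treatment discontinuation.

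**Exposure is small.** Sixty-four subjects enrolled (SAP 7.2), the endpoints are secondary, and Protocol 9.1.2 waives follow-up for several kinds of transition within 28 days of the last dose. This stands.

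**The day-count issue is separate and inferred.** The default is no gap, and the 1401 bound may have been meant to absorb gaps. This stands, and is why confidence there is medium.

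**Stronger readings a reader might infer.** The 1780 of 1815 might suggest that most subjects' Week 96 estimates are contaminated by off-drug values. Step 5 and Section 9.3 do not support that. Nor do the documents show that 1401 is a slip for 1359, or that the overall safety assessment is compromised.

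**Conclusion.** The conflict is in the text and the day arithmetic reproduces. By the rows alone, every on-schedule Part B follow-up without a gap lies in the Week 96 window. The practical effect is limited to spirometry, weight/height/BMI and CFQ-R in subjects with no Week 96 value, the single tie, and whether the Safety Follow-up row is populated. If Section 9.3 governs, the Week 96 estimate is protected. Confidence in this part is high.

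The gap issue holds with medium confidence, because the origin of Part B study day is inferred. If the count is continuous, an on-schedule Part B Week 96 chemistry, hematology, vital-sign, ECG or coagulation value drops out of the by-visit tables after a gap of 15 days (5 if both Week 96 visits run 5 days late). The number of subjects with such a gap is not in the documents. AE, threshold, maximum/minimum and listing outputs are unaffected.

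Both are inexpensive corrections to stated rules and should be made before final programming.

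**What to change.** **1. Precedence.**
- State in footnote 6 that a nominal Safety Follow-up visit, on any day, and an ETT visit after Day 1359 are never used for Week 96, and that the 1401 bound applies only to other records. This keeps genuine late Week 96 values, which a single cut at 1359 would discard.
- State that Section 9.3 governs the Week 96 MMRM and that follow-up values appear only in the descriptive Safety Follow-up row.

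**2. Day count, for visit windowing only.**
- Define Part B study day as (visit date - Part B Day 1) + 673. On-schedule Week 96 then falls on Days 1340-1350 and follow-up on 1360-1384 at any gap length.
- Exclude from post-baseline windows only a separately repeated Part B Day 1 assessment, that is, when Part B Day 1 is more than 1 calendar day after Part A Week 96. Re-based, that record sits on Day 673, where it could displace the Part A Week 96 safety value; it also lies inside the first Part B efficacy window, which opens after Day 667.
- When the two visits are shared, keep the record as Part A Week 96.
- Leave exposure and the treatment-emergent period on calendar dates.

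**Cost.** A SAP appendix edit and re-programming, with no new data. After a gap, the windowing day will differ from the calendar day count, which the SAP should say.
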